8.2 Collection and Documentation of Adverse Events

AEs shall be collected during the clinical study period, from the time of investigational product administration to end of a cohort. Any medical incidences before the administration of the investigational product shall be recorded as current medical history.

AEs shall be reported with details on onset/end date, severity, outcome, action taken to investigational products, causal relationship with investigational products, causal relationship with other drugs, treatment given for AE, and seriousness. When documenting AEs, the investigators should record the overall diagnosis or symptoms using standard medical terms (according to the latest version of the MedDRA).

AEs occurring during the study period shall be followed up until recovery (or stabilization), or until the case is lost to follow up. AEs occurring after the study completion should be reported only when they are serious and causally related to investigational products.

8.3 Assessment of Adverse Events

8.3.1 Severity

The severity of an AE will be determined according to following criteria.

- Mild: Tolerable AEs
(Although signs and symptoms are recognizable, they are easily tolerated, with mild discomfort not causing a loss of time in daily activities; the symptoms do not require treatment or medical assessment, the signs and symptoms are temporary.)
- Moderate: AEs presenting considerable inconvenience to activities of daily living*
(AEs cause a low level of inconvenience or concern to the subject and may interfere with daily activities, but are usually improved by simple therapeutic measures; may cause some interference to functions.)
- Severe: AEs that make activities of daily living* impossible to conduct
(AEs interrupt the subject's normal daily activities and generally require systemic drug therapy or other treatment; they are usually incapacitating.)

* Activities of daily living: all activities that occur in day-to-day life to maintain one's own physical well-being (e.g., Bathing, dressing, eating, taking medications, hygiene maintenance, personal care)

8.3.2 Causal Relationship with Investigational Product

The investigator evaluates all collected AEs based on temporal relationship and his/her clinical judgment. Causal relationships are assessed using the following categories.

- Definitely related

There is clear evidence to suggest a causal relationship, and other possible contributing factors can be ruled out. The temporal order of the investigational product administration and AE incidence is reasonable and the AE cannot be explained by concomitant diseases, other medications, or chemical substances. The AE disappears when the drug is discontinued. Symptoms upon rechallenge (when possible) must be pharmacologically or phenomenologically definitive.

- Probably related

There is evidence to suggest a causal relationship, and the influence of other factors is unlikely. The temporal order of the investigational product administration and AE incidence is reasonable and the possibility of the AE being caused by concomitant diseases, other medications, or chemical substances is low. The AE disappears when the drug is discontinued. Information of rechallenge is not necessary.

- Possibly related

There is some evidence to suggest a causal relationship (e.g., the temporal order of the investigational product administration and AE incidence is reasonable). However, other factors may have contributed to the AE (e.g., the subject's clinical condition, other concomitant events). Although an AE may only be evaluated as "possibly related" soon after occurrence, it can be flagged as requiring more information and later be upgraded to "probably related" or "definitely related".

- Probably not related

AE is deemed to be not causally related to the administration of the investigational product due to their temporal relationship (e.g., temporal order between administration and AE occurrence does not support causality), the AE is reasonably explained by concomitant diseases, other medications, or chemical substances (e.g., the subject's clinical condition, other concomitant treatments).

- Definitely not related

AE is clearly unrelated to the administration of the investigational product and there is clear evidence of a different causal factor. There must be an alternative, and definitive etiology documented by the clinician.

- Unknown

Information is insufficient or contradictory to such an extent that a judgment cannot be made and it is not possible to supplement or verify such information.

8.4 Adverse Event Reporting

8.4.1 SAE Reporting

The principal investigator shall report all SAEs to the sponsor during the clinical study within 24 hours from the time known to the investigator by phone/fax, regardless of causal relationship with the investigational products. SAEs occurring within 14 days after the completion of the study shall be reported by the same process. The investigator must use the subject identification code when reporting SAEs.

Contact information for safety reporting to ISU ABXIS:

PV staff

2

E-mail : [contact] Phone/[contact]
Address : [name]
[name]

Minimum requirements for initial SAE report are as follows.

- Subject information
- Suspected drug and causal relationship with investigational products
- Reporting person information
- Name of SAE

Investigators must conduct follow up reporting when additional information is obtained regarding reported SAEs. The investigator shall report periodically until the SAE is resolved (e.g., recovery or follow-up becomes impossible).

8.4.2 SUSAR Reporting

When a Suspected Unexpected Serious Adverse Reaction (SUSAR) occurs, the principal investigator must report it to the IRB to determine whether the study should be continued or not, and help the sponsor to report the SUSAR immediately to the Ministry of Food and Drug Safety (MFDS).

- Fatal or life threatening SUSARs must be reported immediately. Sponsor has to report them to the MFDS by phone, fax, or documentation, as soon as possible, within 7 days of initial knowledge,

and submit a full report within 15 days of initial knowledge if possible.

- All other SUSARs have to be reported as soon as possible, within 15 days following initial reporting to or knowledge by sponsor.

During the study period, the investigator shall ensure subject safety, and take prompt and proper measures to minimize AEs. The duties of the respective persons-in-charge upon the incidence of SUSARs are as follows.

- Principal investigators: immediately report the SUSAR to the IRB of each center and sponsor, and discontinue the clinical study in part or entirety until further instruction.
- Sub-investigators: immediately report the SUSAR to the principal investigator and sponsor.
- IRB: take measures necessary to the principal investigator (e.g., discontinuation of clinical study in part or entirety)
- Sponsor: upon receiving a SUSAR report from the principal investigators or sub-investigators, immediately submit a copy of the report from the principal investigator or sub-investigator to the MFDS and swiftly inform the study centers

Other AEs not defined above will be tracked until 14 days after the last investigational product administration.

8.5 Pregnancy Reporting

Pregnancy itself during the clinical study will not be regarded as an AE. Selective abortion without complications (not including therapeutic abortion) and hospitalization for the normal delivery of a healthy child are also not considered as AEs.

However, if the subject's spouse or female partner becomes pregnant during the study period (within 30 days from the administration of investigational product), the subject must be immediately dropped out of the study. The investigator shall submit the pregnancy report to the sponsor within 24 hours after the investigator is made aware of pregnancy. Even if the subject withdraws or terminates the study, the investigator shall follow-up the progress of the pregnant woman and her fetus until delivery.

If the pregnant woman experiences a serious complication, natural abortion, extra uterine pregnancy, stillbirth, neonatal death, congenital malformation, etc., these shall be deemed as SAEs, and the investigator shall report them.

9 Ethical, Legal, and Administrative Considerations

9.1 Study Centers

The directors of the study centers shall provide the locations, facilities, and professionals to enable the appropriate execution of the study.

9.2 Institutional Review Boards

When obtaining approval for the protocol or when modifying an approved protocol, the protocol or modified protocol has to be approved by the IRB and the MFDS (if necessary). No subject is allowed to participate in the study prior to approval.

9.3 Subject Information Sheet and Informed Consent Form

Prior to the execution of all study related procedures, the investigator shall fully explain the study to each subject (or the subject's representative), and obtain written consent from the subject.

The investigator shall take enough time to thoroughly assess the eligibility of each subject through interviews and/or tests.

The investigator shall keep the signed original of the informed consent form in the investigator's file, and provide copies of the signed informed consent form and subject information sheet to the subject (or representative). If the subject information sheet and informed consent form are modified, they shall be re-approved by the IRB, as well as the ongoing subject (or representative).

Refer to [Attachment 2. Subject Information Sheet and Informed Consent Form]

9.4 Adherence to the Protocol

The investigator will ensure that the clinical study is conducted in compliance with the Declaration of Helsinki to protect the subject's rights and welfare. The investigator shall be familiar with the Korea Good Clinical Practice (KGCP) and the protocol, and respond actively to subject safety issues.

9.5 Post-study Treatment for Subjects

The investigator shall ensure that a subject who drops out of the study or does not respond to the drug can receive other forms of appropriate treatment.

9.6 Subject Indemnification

The sponsor shall compensate the subject in the case of damages caused by AEs of the investigational product or in the treatment of AEs, where the investigational product is the direct cause of the damage according to Attachment 3. Subject Indemnification.

Refer to [Attachment 3. Subject Indemnification]

9.7 Monitoring

To protect subject's rights and welfare, confirm the accuracy, integrity, and verifiability of data through comparison between reported study related data and source documents, and check if the clinical study has been performed in compliance with the approved protocol and KGCP, the study centers shall be monitored.

The clinical research associate (CRA) from DreamCIS Inc. shall monitor the study, evaluate the study progress, and check whether the investigator's duties are being fulfilled as per the protocol and regulations through routine site visits and phone calls. When visiting the center, the CRA shall check whether the originals of subject's records, CRFs, drug management records, and study-related data (e.g., investigator's files) are being kept, and discuss with the investigator upon finding inconsistencies or problems in the clinical study records.

9.8 Storage of Clinical Study Data

The investigator shall keep the data and records related to the execution of the study in a safe place, maintain their security, and store them for 3 years from the date of product approval in the lastly approved country. After the clinical study report has been completed, documents related to the study shall be transferred to the data storage manager. If the investigator wishes to discard or to move study related records to another place, the investigator shall notify the sponsor in advance.

9.9 Data Safety Monitoring Board and Data Monitoring Committee

An independent Data Safety Monitoring Board (DSMB) and Data Monitoring Committee (DMC) shall perform interim assessments of PK/PD and safety data at the end of each cohort. The DMC assesses the PK/PD data while the DSMB accesses the safety data. The DSMB is comprised of members independent to the study whom include 1 clinician with expertise regarding the clinical aspects of hemophilia (DSMB Chair), 1 clinical pharmacologist, and 1 biostatistician. The DMC is comprised of the investigators of this study, the sponsor, PK/PD experts, and etc.

Upon the termination of each cohort (after the last visit of the final subject), the PK/PD and safety data are analyzed before decisions are made regarding the commencement of the next cohort, target dose, and blood collection period. In the presence of subject safety concerns, the study may be put on hold or terminated, and decisions regarding the necessity of additional subjects as well as subject/cohort replacement/suspension may also be made. Ad hoc specialists may be invited to participate as non-voting members of DSMB at any time if additional expertise is needed.

9.10 Audit and Inspection

To ensure that the KGCP and all related regulations are observed, the sponsor or a person authorized by the sponsor may perform audits while the MFDS may conduct inspections of the study. After the relevant notice is given to the investigator, the investigator shall respond to audit or inspection requests, allow the auditor or inspector direct access to all clinical study related documents, and consent to allocating sufficient time to fully discuss all observations and related issues.

10.1 Derivation	21
10.2 Categorization	22
Appendix.....	25

Abbreviations

Abbreviations	Definition
ADR	Adverse Drug Reaction
AE	Adverse Event
AESI	Adverse Event of Special Interest
CS	Clinical Significance
FIX	Factor IX
HIV	Human Immunodeficiency Virus
IP	Investigational Products
IU	International Unit
MedDRA	Medical Dictionary for Regulatory Activities
NCS	Non Clinical Significance
PT	Preferred Term
SAP	Statistical Analysis Plan
SAS	Statistical Analysis System
SOC	System Organ Class
TLFs	Tables, Listings, Figures
WHODDE	World Health Organization Drug Dictionary Enhanced

1. Purpose of the Statistical Analysis Plan

The purpose of this document is documentation for the details for analyzing the data collected in the ISU304-001 study.

This document is based on the statistical analysis method described in protocol, and results of the analysis in this document will be included in the clinical study report.

If any additional analysis undescribed in this document is required, it will be written in separate document (ex. Additional Analysis Plan).

2. Study Features

Study title	A Phase 1, Open-label, Multi-center, Dose-escalation Study to Investigate the Safety, Pharmacokinetics and Pharmacodynamics of ISU304 in Previously Treated Hemophilia B Patients
Study duration	Approximately 24 months after the protocol approval from the institutional review boards (IRBs)
Indication	Previously treated hemophilia B patients
Study objective	To investigate the safety, pharmacokinetics and pharmacodynamics of ISU304 (recombinant factor IX with increased activity) in previously treated hemophilia B patients
Phase and design	Phase 1, open-label, multi-center, dose-escalation
Investigational products	
 • Study drug: ISU304 75, 150IU/kg, intravenous or subcutaneous administration • Active control: BeneFIX 75 IU/kg, intravenous administration • Rescue drug: Treatment currently used by subject to treat hemophilia B

Administration and follow-up period	
 Cohort 1 (n=3): 7 days Single intravenous administration of BeneFIX (75 IU/kg) with 72 hours of observation, followed by single intravenous administration of ISU304 (75 IU/kg) with 72 hours of observation Cohort 2 (n=3): 7 days Single intravenous administration of ISU304 (75 IU/kg) with 72 hours of observation, followed by single subcutaneous administration of ISU304 (75 IU/kg) with 72 hours of observation Cohort 3 (n=3): 9 days Single intravenous administration of ISU304 (75 IU/kg) with 72 hours of observation, followed by single subcutaneous administration of ISU304 (150 IU/kg) with 120 hours of observation Cohort 4 (n=5): 10 days Single subcutaneous administration of ISU304 (150 IU/kg) per day for 6 days with 240 hours of observation Cohort 5 (n=minimum 3, maximum 5): 15 days Single intravenous administration of ISU304 (75 IU/kg) is followed by subcutaneous ISU304 (150 IU/kg) administration for 9 days with 312 hours of observation
Planned number of subjects	At least 12 subjects (including duplication)
Inclusion criteria	
 Previously treated male patients with moderate or severe hemophilia B (documented FIX activity \leq 2% and exposed to any FIX product for \geq 150 exposure days (estimated)) Patients must be 12 to 65 years old at the time of screening Patients who have discontinued a previously treated FIX product at least 4 days prior to the administration of investigational product HIV negative, or if HIV positive with a CD4 count $>$ 200/μL (documented $<$ 200 particles/μL or \leq 400,000 copies/mL) at the time of screening Voluntary consent to participate in the study
Exclusion criteria	
 Patients with a history or a family history of FIX inhibitors Patients with FIX inhibitors (positive result for BeneFIX or ISU304 from inhibitor tests) at the time of screening Patients who have a history of thromboembolic events (myocardial infarction, cerebrovascular disease, venous thrombosis, etc.) Patients with known hypersensitivity, allergy, or anaphylaxis to any FIX

	
product or hamster protein
 
5) Patients receiving treatment with a FIX product or a bypass agent within 4 half-lives for the agent used (at least 96 hours) prior to the administration of the investigational product
 
6) Patients who have been exposed to long-term administration(exceeding 14 days) of immunomodulating agents or immunosuppressants such as α-INF or adrenocortical hormones over the past 3 months or who are currently receiving or planning to receive such treatment during the study period
 
7) Patients who have been administered vaccines during the period of 6 months prior to the administration of the investigational product or plan to receive vaccines during the study period
 
8) Patients with any other co-existing bleeding disorder (Von Willebrand disease, etc.)
 
9) Patients with positive D-dimer results ($\geq 0.5 \mu\text{g/mL}$) at the time of screening
 
10) Patients with platelet counts less than $100,000/\mu\text{L}$ at the time of screening
 
11) Patients with ALT, AST levels 5 times greater than upper normal limit or total bilirubin, serum creatinine levels 2 times greater than upper normal limit at the time of screening
 
12) Active hepatitis patients who are clinically significant HBs Ag positive or anti-HCV Ab positive at the time of screening
 
13) Patients scheduled for surgery during the study period
 
14) Patients participated in another study within 30 days before screening or scheduled to participate in any other study during the study period

Safety endpoints	
 Adverse events after the administration of investigational products (local/systemic/other) Physical examination Vital signs Electrocardiogram Laboratory tests FIX inhibitors (or neutralizing antibodies) and anti-drug antibodies to investigational products
Other endpoints	Demographic data, hemophilia B status, medical history, medication history

Analysis method	
• Analysis population
- Safety analysis set: All subjects who receive at least one dose of investigational products- PK set: Subjects in the safety analysis set who complete all procedures planned for the cohort and for whom PK samples have been obtained at least 4 times after administration.• PK Analysis: Using WinNonlin software (Pharsight, CA, USA)• Bioavailability analysis for subcutaneous administration• Other statistical analysis
- For each cohort, descriptive statistics will be given for each endpoint for each subject using SAS software (SAS Institute Inc, Cary, USA)
-----------------	--

3. Sample Size Calculation

At least 12 subjects who meet all of the inclusion criteria and none of the exclusion criteria including duplication will be enrolled.

4. Sequence of Planned Analyses

4.1 Interim Analysis

Interim analysis is not planned in this study.

4.2 Final Analysis

The statistical analysis of this study will be performed after all data is collected and database lock is completed.

5. Changes to the Planned Analyses in the Protocol

The PK/PD analysis is described in Protocol but PK/PD analysis will be conducted at the designated central laboratory (HTI). So this document does not include this analysis.

6. Analysis Sets

Safety Analysis Set

All subjects who receive at least one dose of investigational products

7. Protocol Deviations

The additional protocol deviations other than analysis set criteria described in '6. Analysis Sets' are not considered.

8. General Specifications for Statistical Analyses

8.1 Analysis Software

All statistical analysis will be carried out with SAS Software (SAS Institute Inc, Cary, USA) version 9.4 or more recent version.

8.2 Multiple Comparison and Multiplicity

The consideration of multiple comparison and multiplicity is not necessary in this study.

8.3 Planned Subgroup

Subgroup analysis is not planned in this study.

8.4 Planned Covariate

Covariate analysis is not planned in this study.

8.5 Summary Statistics

For the continuous data, descriptive statistics such as mean, standard deviation, 25th percentile, median, 75th percentile, minimum and maximum value shall be obtained. For the categorical data,

descriptive statistics such as frequency and percentage shall be provided.

8.6 Methods for Missing Data and Incomplete Data

Missing data and incomplete data will not be replaced.

Exceptionally in laboratory test, if results include incomplete data, it will be converted to numeric value and included in the analysis as following example. Also incomplete data will be listed.

- if data including '<number', it will be replaced 'number - 0.001' (e.g. <2 → 1.999).
- if data including '>number', it will be replaced 'number + 0.001' (e.g. >100 → 100.001).

8.7 Other Statistical Considerations

The analysis will be carried out according to considerations as follows. If additional considerations on each analysis item is required, the corresponding options will be described in '10.1 Derivation'.

- In Cohort 1, Cohort 2, Cohort 3, 'Baseline' is '1st Hospitalization (Before 1st injection)' visit. And in Cohort 4 and Cohort 5, 'Baseline' is 'Before 1st injection' visit.
- The criteria for converting day to month are as follows: 1month=30days
- When calculating percentage for categorical variables except for 'Analysis Sets' summary, the denominator is the number of subjects in each cohort. Only in case of analysis by type of Medical History/Surgical History/Prior Medication/Concomitant Medication, the denominator is the number of subjects having Medical History/Surgical History/Prior Medication/Concomitant Medication in each cohort.
- The calculating criteria of percentage for 'Analysis Sets' summary will be described in 9.1 Disposition of Subjects'.
- The 95% confidence interval will be estimated by using exact method.

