4.4 Administration of Investigational Products and Follow Up Periods

- Cohort 1 (n=3) : 7 days
Single intravenous administration of BeneFIX (75 IU/kg) with 72 hours of observation, followed by single intravenous administration of ISU304 (75 IU/kg) with 72 hours of observation
- Cohort 2 (n=3) : 7 days
Single intravenous administration of ISU304 (75 IU/kg) with 72 hours of observation, followed by single subcutaneous administration of ISU304 (75 IU/kg) with 72 hours of observation
- Cohort 3 (n=3) : 9 days
Single intravenous administration of ISU304 (75 IU/kg) with 72 hours of observation, followed by single subcutaneous administration of ISU304 (150 IU/kg) with 120 hours of observation
-
- Cohort 4 (n=5) : 6 days
Single subcutaneous administration of ISU304 (150 IU/kg) per day for 6 days with 144 hours of observation
* At least 5 Subjects including the subjects from Cohorts 1 ~ 3 are expected to participate in Cohort 4.
- Cohort 5 (n=3~5) : 15 days
Single intravenous administration of ISU304 (75 IU/kg) is followed by subcutaneous ISU304 (150 IU/kg) administration for 9 days with 312 hours of observation

The baseline for all cohorts will be at the time before the intravenous or subcutaneous administration of the investigational products. Additional subjects may be enrolled in all cohorts or cohorts may be canceled depending on the results of PK/PD analysis. 14 days are allowed from the first

administration of the study drug to the second administration in cohorts 1 to 4 depending on the condition of subjects. If bleeding occurs 72 hours after first administration in cohorts 1 to 4 and FIX product is administered as a rescue medication, there must be at least of 4 days of wash-out period from the last administration of FIX.

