5.2.1.5 Visit 4 (Day 3 to 5) - 2nd Hospitalization

Visit 4 is for the 2nd administration of the study drug, and the subject is hospitalized for a day as in Visit 1. The subject is recommended to visit the hospital to be hospitalized on the day before the administration. The timing of the 2nd administration is also identical to the time that the subject will have to visit the hospital on subsequent visits. Thus the time of the 2nd administration should be determined with consideration for the subject's schedule.

An interval of at least 4 days is required between the administration of the 1st and 2nd doses. The investigator shall schedule the visit in consideration of this interval. Depending on the schedule, the procedure for Visits 3 and 4 could be conducted on the same day. Should this be the case, all procedures for the respective visits must be carried out without fail. The investigator must observe the administration site for at least 30 minutes to 1 hour after the administration of investigational product for AEs. The following is the procedure for Visit 4.

2nd hospitalization (Day 3 to 4)

- ① Hospitalization procedure for subject
- ② Checking for AEs and concomitant medications
- ③ Electrocardiogram
- ④ Blood/urine sample collection for laboratory tests, FIX inhibitor test, anti-drug antibody test, and Bethesda assay

2nd administration and blood collection for PK/PD analysis (Day 4)

- ① Checking for AEs and concomitant medications
- ② Physical examination, assessment of vital signs
- ③ Blood sample collection for PK/PD analysis before administration of investigational product
- ④ Administration of investigational product
For Cohort 1, ISU304 75 IU/kg, intravenous administration
For Cohort 2, ISU304 75 IU/kg, subcutaneous administration
- ⑤ Checking for AEs at least 30 min to 1 hr after investigational product administration
- ⑥ Blood sample collection for PK/PD analysis
For Cohort 1,
: 0(right after administration)hr±1min, 0.25hr±3min, 0.5hr±3min, 1hr±3min, 3hr±5min, 6hr±5min, 9hr±5min
For Cohort 2,
: 1hr±3min, 2hr±3min, 4hr±5min, 6hr±5min, 8hr±5min, 10hr±5min, 12hr±5min
- ⑦ Physical examination, assessment of vital signs, sample collection for blood coagulation test 6 hours after administration

2nd discharge (Day 5)

- ① Checking for AEs and concomitant medications
- ② Physical examination, assessment of vital signs
- ③ Blood sample collection for PK/PD analysis
24hr±15min

- ④ Sample collection for blood coagulation test

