9.5.2 Laboratory Tests

For laboratory test, the descriptive statistics for each cohort will be presented in collected visit. And the change of baseline and end of cohort will be presented.

Additionally, the frequency and percentage of 'Normal/NCS', 'CS' in CD4 count of hematology test at screening will be presented. And the frequency and percentage of 'Normal', 'NCS', 'CS' in serology test at screening will be presented.

Also, 'Normal/NCS', 'CS' changes from baseline to end of cohort in hematology test(except for CD4 count), blood chemistry test, urinalysis and blood coagulation test will be summarized in terms of frequency and percentage by cohort.

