9.5.5 Electrocardiogram

For each electrocardiogram results, the descriptive statistics for each cohort will be presented at each collected visit. And the change of baseline and end of cohort will be presented.

'Normal/NCS', 'CS' changes from baseline to end of cohort in electrocardiogram results will be summarized in terms of frequency and percentage by cohort.

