9.5.6 FIX Inhibitor and Anti-drug Antibody Test

For FIX Inhibitor test and Anti-drug Antibody test, 'Positive', 'Negative' changes from 'Before injection' to 'After injection' in each results will be summarized in terms of frequency and percentage by cohort. If 'Positive' is confirmed once after injection, the subjects will be included 'Positive'.

In FIX Inhibitor test, if data is collected as 'LOQ', it will be analyzed as 'Negative', and if data is collected any numeric value, it will be analyzed as 'Positive'.

In Anti-drug Antibody test, data is collected as 'Positive', 'Negative'.

Additionally all FIX Inhibitor test and Anti-drug Antibody test results will be listed.

10. Derivation and Categorization for Variable

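### A single baseline before dose 1 leaves Cohort 1 with no ISU304-only change or shift, and the antibody before/after split does not say which injection it means

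*Combined protocol and SAP*

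**What the plan says.** SAP 8.7 sets the reference point for the two-period cohorts: "In Cohort 1, Cohort 2, Cohort 3, 'Baseline' is '1st Hospitalization (Before 1st injection)' visit". For laboratory values SAP 9.5.2 adds: "And the change of baseline and end of cohort will be presented". For ECG, SAP 9.5.5 has both a change and a shift, the latter worded "Normal/NCS', 'CS' changes from baseline to end of cohort in electrocardiogram results will be summarized in terms of frequency and percentage by cohort". SAP 9.5.3 (physical examination) has a shift between the same two points, and SAP 9.5.4 (vital signs) a change between them.

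The Cohort 1 sequence, in protocol 4.4 and SAP section 2, reads "Single intravenous administration of BeneFIX (75 IU/kg) with 72 hours of observation, followed by single intravenous administration of ISU304 (75 IU/kg) with 72 hours". Cohorts 2 and 3 receive ISU304 intravenously and then subcutaneously.

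For antibodies, SAP 9.5.6 does not use the word baseline. It plans "Positive', 'Negative' changes from 'Before injection' to 'After injection' in each results will be summarized in terms of frequency and percentage by cohort", and adds "If 'Positive' is confirmed once after injection, the subjects will be included 'Positive". It does not say which injection is meant.

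The protocol collects a second pre-dose set. At the 2nd hospitalisation, protocol 5.2.1.5 lists an ECG and "Blood/urine sample collection for laboratory tests, FIX inhibitor test, anti-drug antibody test, and Bethesda assay". Protocol 5.1.9 adds coagulation tests on that day, and physical examination and vital signs are repeated just before dose 2. Protocol 5.2.2.5 does the same for Cohort 3.

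**The concern.** The study objective is the safety, PK and PD of ISU304. Cohort 1 is where ISU304 is first given and is the only cohort with a comparator. If its calculated changes run from before BeneFIX to after ISU304, a laboratory or ECG shift in that cohort cannot be assigned to one product from the change and shift tables. The measurements that would separate the two are taken, but the SAP never uses them as a reference.

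The antibody split raises a related problem. Protocol 5.1.15 makes inhibitor generation or seroconversion an event of special interest. If the dividing injection is simply the first one, an ISU304-antibody positive found before any ISU304 exposure would enter the frequency table as a result after injection.

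**Working it through.** The plan gives no figure to reproduce. The check sets the SAP rules against the Cohort 1 visit schedule.

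**1. What the change and shift cover.** Inputs: doses at least 4 days apart (protocol 5.2.1.5); up to 14 days allowed (protocol 4.4); end of cohort 72 h, or 3 days, after dose 2 (protocol 5.2.1.7). Counting from dose 1, the interval is gap + 3 days, and the share before any ISU304 is gap / (gap + 3).

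- Shortest gap: 4 / (4 + 3) = 4/7 = 57%.
- Longest gap: 14 / (14 + 3) = 14/17 = 82%.

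More than half of each Cohort 1 interval therefore precedes ISU304. No period-2 baseline appears in SAP 8.7, 9.5 or 10.1.

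**2. How many places are affected.** Planned places by cohort: 3 + 3 + 3 + 5 + (3 to 5) = 17 to 19. Products are mixed only in Cohort 1, which is 3 of these. The 6 places in Cohorts 2 and 3 mix routes of the same product. Cohorts 4 and 5 are outside this point.

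**3. Where the ISU304-antibody samples fall in Cohort 1.** Times are from protocol 5.1.10 and 5.2.6.

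| Sample | Plain reading of SAP 9.5.6 | Relative to first ISU304 dose |
|---|---|---|
| Screening, 1st hospitalisation | before | before |
| Interim visit, 72 h after BeneFIX | after | before |
| 2nd hospitalisation | after | before |
| End of cohort, 72 h after ISU304 | after | after |
| Post-study visit (optional) | after | after |

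On that reading, 2 of the 4 samples counted as after precede any ISU304, or 2 of 3 if the optional visit is missed. The reading is the plain one because SAP 8.7 uses the term 1st injection for the first dose in every two-period cohort, which in Cohort 1 is BeneFIX, and protocol 2.1.2 lists BeneFIX among the investigational products.

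**4. Illustration.** Suppose one Cohort 1 subject has an ISU304-antibody positive only at the interim visit or 2nd hospitalisation. The table would show 1/3 = 33.3%; counted from the first ISU304 dose it is 0/3. Exact (Clopper-Pearson) 95% limits:

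- 0/3: upper limit 1 − 0.025^(1/3) = 70.8%, so 0 to 70.8%.
- 1/3: lower limit 1 − 0.975^(1/3) = 0.8%; upper limit solves (1−p)³ + 3p(1−p)² = 0.025, giving 90.6%.

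SAP 9.5.6 plans no interval for this table. These limits only show how little three subjects can say.

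**The case against.** Much of the missing picture can be recovered. SAP 9.5.2, 9.5.4 and 9.5.5 summarise laboratory values, vital signs and ECG at each visit where they are collected. For laboratory values and ECG this includes the interim visit and 2nd hospitalisation. With complete data on three subjects, the mean change over period 2 can be read off by subtraction. All inhibitor and anti-drug antibody results are listed, the two products' antibodies are tested separately, and protocol 5.1.10 requires a confirmatory test for a positive inhibitor result. The study is descriptive, and the SAP's mock-up tables, which are not shown, might add detail.

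This stands as mitigation but is not complete. Visit means do not give the spread of within-subject change. A shift between two end points cannot show whether a lasting abnormality began after BeneFIX or after ISU304, and it misses one that resolved. SAP 9.5.3 plans no by-visit summary for physical examination, only the shift and a listing of clinically significant results. A listing does not correct the antibody frequency table, and protocol 5.1.10 describes no confirmatory step for the anti-drug antibody ELISA.

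A reader might also infer that the SAP departs from the protocol without declaring it. The text does not show that. Protocol 4.4 says "The baseline for all cohorts will be at the time before the intravenous or subcutaneous administration of the investigational products", which does not say each administration and names no second baseline. Protocol 7.2.3 plans its safety summaries before and after the investigational products, mostly by cohort. One baseline per cohort is a permissible reading.

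**Conclusion.** The point holds as a gap in the change, shift and antibody rules. It does not mean that information is lost. In Cohort 1 (3 of 17 to 19 places) no ISU304-only change or shift is calculated, and 57% to 82% of the interval precedes ISU304. In Cohorts 2 and 3 the product is not in doubt and only the route is merged.

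Three stronger conclusions are tempting but unsupported. The by-visit summaries mean it is too much to say that nothing about ISU304 can be learned from Cohort 1. It is also wrong to treat all nine places in Cohorts 1 to 3 as mixing products. And SAP 9.5.6 leaves its injection undefined, so it is not certain that positives before ISU304 will be counted as after. That is the plain reading, and an ISU304-specific one is written nowhere.

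The 1/3 against 0/3 comparison is hypothetical. The order in Cohort 1 is fixed, so even a period-2 change follows BeneFIX by 4 to 14 days. It describes change after ISU304 but does not exclude carry-over.

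**What to change.** - **SAP 8.7:** keep the present baseline for period 1 and add a period-2 baseline for Cohorts 1 to 3, namely the last value before dose 2.
- **SAP 9.5.2 to 9.5.5:** report change and shift for laboratory tests, ECG, vital signs and physical examination by period (dose 1 to interim visit; dose 2 to end of cohort), labelled with the product and route given. The main gain is separating BeneFIX from ISU304 in Cohort 1.
- **SAP 9.5.6:** define before and after relative to the first dose, within the cohort, of the product whose antibody is tested. For ISU304 antibodies in Cohort 1, the samples up to and including the 2nd hospitalisation are then before, and the end-of-cohort and post-study samples are after.
- **Do not split antibody results by route in Cohorts 2 and 3.** Dose 2 may follow dose 1 by only 4 days, and end of cohort is 72 h (Cohort 2) or 120 h (Cohort 3) after dose 2. A conversion first seen then could come from either dose.

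The cost is SAP wording and programming. No visit, sample or subject is added.
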